7.2. Classification of Adverse Events

7.2.1. Relationship to Study Drug

The investigator will review each event and assess its relationship (unrelated, unlikely, possibly, probably, definitely) to drug treatment. The following definitions will be used for these causality assessments.

Unrelated	
 • The AE must clearly be caused by the subject's clinical state, or the study procedure/conditions. • Definitely not related to drug. • Temporal sequence of an AE onset relative to administration of drug not reasonable. • Another obvious cause of an AE.
Unlikely	
 • Time sequence is unreasonable. • There is another more likely cause for an AE.
Possibly	
 • Corresponds to what is known about the drug. • Time sequence is reasonable. • Could have been due to another equally, likely cause.
Probably	
 • Is a known effect of the drug. • Time sequence from taking drug is reasonable. • Ceases on stopping the drug. • Cannot be reasonably explained by the known characteristics of the subject's clinical state.
Definitely	
 • Is a known effect of the drug (e.g., listed in IB). • Time sequence from taking drug is reasonable. • Event stops upon stopping drug, event returns upon restarting drug. NOTE: Re-challenge will only be considered after consultation with the medical monitor and the sponsor.

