7.2.3. Expectedness

For this study, all AEs will be recorded.

The safety and tolerability of BTX 1204 4% (w/w) Solution was evaluated in a Phase 1b study in subjects with mild to moderate atopic dermatitis. This study demonstrated that BTX 1204 4% was safe and well tolerated with up to 3 mL applied BID for up to 28 days. Adverse events reported as related to study drug treatments were administration site conditions including application site erythema, application site pruritus, and application site pain.

Studies of the active ingredient (CBD) administered orally in multiple therapeutic settings has described no consistent findings for systemic AEs. Based on findings in previous studies of CBD, mild skin irritation may occur (see IB for details).

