7.5. Safety Oversight

Oversight of the safety of the study will be the responsibility of the Medical Monitor. No Data Safety Monitoring Board (DSMB) will be convened for this study. Safety data will be regularly reviewed (monthly at a minimum). If unexpected safety signals are observed, the Medical Monitor, the sponsor, and the HREC/IRB, if necessary, will determine if the study requires a pause to further assess the safety signal or termination.

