b Percentages based on the number of subject in the safety population with percent compliance calculated.

SOURCE: USERNAME/SPONSOR/PROJECT/JOBNAME (DATE,TIME)

Table 14.3.0.1: Summary of Extent of Exposure  
(Safety Population)  
(Page 2 of 2)

	BTX 1204 4% BID (N=xxx)	Vehicle BID (N=xxx)
Percent Compliance		
n	xx	xx
Mean	xx.x	xx.x
SD	xx.xx	xx.xx
Median	xx.x	xx.x
Min., Max.	xx, xx	xx, xx
Compliant a		
Yes b	xx ( xx.x%)	xx ( xx.x%)
No b	xx ( xx.x%)	xx ( xx.x%)

a Compliant with the dosing regimen is if the subject applied at least 80% but no more than 120% of expected applications while enrolled in the study.

b Percentages based on the number of subject in the safety population with percent compliance calculated.

SOURCE: USERNAME\SPONSOR\PROJECT\JOBNAME (DATE,TIME)

Table 14.3.1.1: Summary of Treatment-Emergent Adverse Event Characteristics  
(Safety Population)

	BTX 1204 4% BID (N=xxx)	Vehicle BID (N=xxx)
Number (%) of Subjects Reporting At Least One Treatment-Emergent Adverse Event	xx ( xx.x%)	xx ( xx.x%)
Number of Treatment-Emergent Adverse Events	xx	xx
Number (%) of Subjects Reporting At Least Once Serious Treatment-Emergent Adverse Event	xx ( xx.x%)	xx ( xx.x%)
Number of Serious Treatment-Emergent Adverse Events	xx	xx
Number (%) of Subjects who Discontinued Study Due to At Least One Treatment-Emergent Adverse Event	xx ( xx.x%)	xx ( xx.x%)
Number of Treatment-Emergent Adverse Events Leading to Discontinuation of Study	xx	xx
Maximum Severity		
Severe	xx ( xx.x%)	xx ( xx.x%)
Moderate	xx ( xx.x%)	xx ( xx.x%)
Mild	xx ( xx.x%)	xx ( xx.x%)
Strongest Relationship to Study Drug		
Related	xx ( xx.x%)	xx ( xx.x%)
Not Related	xx ( xx.x%)	xx ( xx.x%)

Note: Treatment-emergent adverse events are those with an onset on or after the date of first application of study drug.

Percentages are based on the number of subjects in each treatment group in the Safety population.

Related adverse events include possibly, probably, and definitely responses to relationship to study drug question.

SOURCE: USERNAME\SPONSOR\PROJECT\JOBNAME (DATE,TIME)

Table 14.3.1.2: Summary of Treatment-Emergent Adverse Event by MedDRA System Organ Class and Preferred Term (Safety Population)

System Organ Class a Preferred Term	BTX 1204 4% BID (N=xxx)	Vehicle BID (N=xxx)
System Organ Class 1	xx ( xx.x%)	xx ( xx.x%)
Preferred Term 1	xx ( xx.x%)	xx ( xx.x%)
Preferred Term 2	xx ( xx.x%)	xx ( xx.x%)

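### Protocol 7.2.1 lists prior knowledge of the effect in every category that the SAP counts as Related, so a new drug reaction may fit no causality category

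*Protocol*

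**What the plan says.** Protocol 7.2.1 has the investigator assign each AE to one of five categories and makes the wording binding: "The following definitions will be used for these causality assessments". Each category is a bullet list.

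- **Possibly:** "Corresponds to what is known about the drug"; reasonable timing; "Could have been due to another equally, likely cause".
- **Probably:** the effect is already recognised for the drug; reasonable timing; the event ends when the drug is stopped; the subject's clinical state does not explain it.
- **Definitely:** "Is a known effect of the drug (e.g., listed in IB"; reasonable timing; the event stops on stopping and returns on restarting.
- **Unlikely:** unreasonable timing; "There is another more likely cause for an AE".
- **Unrelated:** a clear non-drug cause; certainty that the drug is not involved; unreasonable timing; another obvious cause.

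The footnote to SAP Table 14.3.1.1, repeated for Table 14.3.1.4, says: "Related adverse events include possibly, probably, and definitely responses to relationship to study drug question". Table 14.3.1.1 has one other relationship row, Not Related, so Unlikely and Unrelated fall there by elimination. SAP 6.4.5 keeps in the per-protocol (PP) set subjects who discontinue because of an AE related to treatment. Expectedness has its own heading, Protocol 7.2.3.

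**The concern.** Causality asks whether the drug brought about this event in this subject. Expectedness asks whether the effect was already on record. When prior knowledge is a criterion in every positive causality category, an effect seen for the first time has no obvious place among them.

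The set of recognised effects is small here. Protocol 7.2.3 names application-site reactions as the treatment-related events in the Phase 1b study and reports no consistent systemic findings with oral CBD. If investigators take the prior-knowledge criterion literally, the related-TEAE summaries could under-report effects not seen before. The PP set could also lose a subject who stopped because of such an event.

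**Working it through.** No arithmetic applies; the check is to run one event through the five definitions.

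**Event A:** not previously known for the drug, reasonable timing, resolves on stopping, no other cause, no rechallenge.

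| Category | Criteria that event A meets | Fits if all are required | Fits if any one is enough |
|---|---|---|---|
| Unrelated | 0 of 4 | No | No |
| Unlikely | 0 of 2 | No | No |
| Possibly | 1 of 3 (timing) | No | Yes |
| Probably | 3 of 4 (timing, resolution, not explained by clinical state) | No | Yes |
| Definitely | 1 of 3 (timing) | No | Yes |

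1. **All criteria required.** Event A fits 0 of the 3 related categories and 0 of 5 overall. The only criterion it misses for Probably is prior knowledge. The same event with the same course would be Probably related if it were already on record (4 of 4). That is expectedness deciding causality.

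2. **Any one criterion enough.** Reasonable timing alone qualifies event A for Possibly, Probably and Definitely at once. The gap disappears, but the scale no longer separates its three upper grades.

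3. **Which reading applies.** Protocol 7.2.1 does not say. The severity table in 7.2.2 states when its items are alternatives; the causality table has no such note. Only the cumulative reading lets the scale discriminate.

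4. **The softer wording in Possibly.** Correspondence with what is known could be taken as pharmacological plausibility. Event A might then meet that criterion, giving 2 of 3. It would still miss the criterion about an equally likely other cause, because it has none.

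5. **Unlikely and Unrelated.** Event A meets none of their criteria, so it fits neither on either reading.

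6. **Deleting the prior-knowledge criteria alone.** Event A then meets all of Probably. Now take **event B**, identical except that it persists after stopping. It fails Probably (no resolution), Definitely (no stop and return) and Possibly (no equally likely cause). Read cumulatively, it still fits 0 of 5. A repair must deal with these criteria as well.

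**The case against.** **The gap depends on an unstated rule.** If one criterion is enough, event A qualifies as related. This stands as a limit on the claim. It is not a defence of the table, because that reading leaves a scale that does not discriminate.

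**Possibly does not demand an established effect.** This also stands. What is known can include pharmacology and nonclinical findings, some of which Protocol 1.3.1 describes. It would therefore be wrong to say that every related category requires an effect already on record.

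**A reader might infer that new reactions are forced into Not Related.** The documents do not support this. Unlikely and Unrelated fail to describe event A just as the other categories do. An investigator with no fitting category may choose one of them, but the text does not direct it.

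**A reader might infer that safety oversight is disabled,** because Protocol 7.5 says "If unexpected safety signals are observed, the Medical Monitor, the sponsor, and the HREC/IRB, if necessary, will determine if the study requires a pause". That sentence sets no causality condition, and it is not the only route to a pause: Protocol 4.4 separately allows suspension. AEs are recorded whatever their suspected cause (7.3), and SAEs go to the sponsor within 24 hours whether or not judged related (7.4.2). Safety data are reviewed at least monthly (7.5), and blinded data in real time (11.1.6). SAP 6.11.2 summarises all TEAEs, serious TEAEs and TEAEs leading to discontinuation by treatment group, without regard to attribution. The randomised vehicle comparison in those tables can show a new effect.

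**A reader might try to size the problem from limited earlier exposure.** Protocol 7.2.3 says of Phase 1b: "This study demonstrated that BTX 1204 4% was safe and well tolerated with up to 3 mL applied BID for up to 28 days". The responder percentages in Protocol 1.3.2 fit 8/23 = 34.8% and 2/11 = 18.2%. With no event in 23 treated subjects, the upper 95% bound is 1 − 0.05^(1/23) = 12.2%. But 23 + 11 = 34, while Protocol 1.1 reports 37 treated; with 26 on active the bound is 10.9%. The present maximum allowance is 7 mL × 2 × 30 mg/mL = 420 mg/day, or 35.28 g over 84 days, against 180 mg/day × 28 days = 5.04 g, a ratio of 7.0. That compares maximum allowances, not expected use. Neither figure measures how often an event would be misclassified.

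**Conclusion.** The concern holds in a limited form. Each category that the SAP counts as Related lists prior knowledge of the effect, more softly in Possibly than in Probably and Definitely, and the rule for combining criteria is missing. If all criteria are required, a new event with reasonable timing, no other cause and resolution on stopping has no category. Not Related is then a possible default.

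The reach is narrow: the relationship rows of Table 14.3.1.1, Table 14.3.1.4, and the PP rule for discontinuation due to a related AE. The PP analyses are supportive only, and the rule matters only for a subject who stops because of a new event coded as not related. The documents give no basis for estimating how many events or subjects this would involve. The conclusion assumes the cumulative reading and investigators who apply the criteria literally.

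**What to change.** In Protocol 7.2.1:

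- Remove prior knowledge as a condition for Possibly, Probably and Definitely. It may remain as supporting evidence.
- State how the criteria within a category combine.
- Reword Possibly so that an event with reasonable timing and no more likely other cause qualifies, whether or not the effect is already known and whether or not it ends when the drug is stopped. This covers event B as well as event A.
- State that lack of prior knowledge is not a reason to choose Unlikely or Unrelated.
- Judge expectedness separately, under 7.2.3, against the Investigator's Brochure.

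The cost is wording in one protocol table, a sentence in 7.2.3 and a matching change to the eCRF completion guideline. The SAP's Related and Not Related grouping can stay as it is. The downside is that the count of related events may rise slightly.

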7.2.2. Severity of Event

Each sign or symptom reported will be graded on a 5-point severity scale (Grade 1, 2, 3, 4 and 5).

The following definitions for rating severity will be used:

Grade 1	Mild; asymptomatic or mild symptoms; clinical or diagnostic observations only; intervention not indicated.
Grade 2	Moderate; minimal, local or noninvasive intervention indicated; limiting age-appropriate instrumental activities of daily living.*
Grade 3	Severe or medically significant but not immediately life-threatening; Hospitalisation or prolongation of hospitalisation indicated; disabling; limiting self-care activities of daily living.** Note: An experience may be severe but may not be serious, (e.g., severe headache).
Grade 4	Life-threatening consequences; urgent intervention indicated.
Grade 5	Death related to AE.

Note: A semi-colon indicates 'or' within the description of the grade.

*Instrumental activities of daily living refer to preparing meals, shopping for groceries or clothes, using the telephone, managing money, etc.

**Self-care activities of daily living refer to bathing, dressing and undressing, feeding self, using the toilet, taking medications, and not bedridden.

7.2.3. Expectedness

For this study, all AEs will be recorded.

The safety and tolerability of BTX 1204 4% (w/w) Solution was evaluated in a Phase 1b study in subjects with mild to moderate atopic dermatitis. This study demonstrated that BTX 1204 4% was safe and well tolerated with up to 3 mL applied BID for up to 28 days. Adverse events reported as related to study drug treatments were administration site conditions including application site erythema, application site pruritus, and application site pain.

Studies of the active ingredient (CBD) administered orally in multiple therapeutic settings has described no consistent findings for systemic AEs. Based on findings in previous studies of CBD, mild skin irritation may occur (see IB for details).

7.3. Time Period and Frequency for Event Assessment and Follow-up

All AEs occurring after signing of the consent form through completion of Day 85 Visit will be recorded. AEs arising after the time of initiation of first treatment with study drug will be considered treatment emergent AEs (TEAEs). At each contact with the subject, the investigator

or designee must seek information on AEs by non-leading specific questioning and, as appropriate, by examination. All observed or volunteered AEs, regardless of suspected causal relationship to study drug, must be recorded on the AE page of the eCRF.

The occurrence of an AE or SAE may come to the attention of study personnel during study visits and interviews of a study subject presenting for medical care, or upon review by a study monitor. All AEs including local and systemic reactions not meeting the criteria for SAEs will be recorded. Information to be collected includes event description, time of onset, clinician's assessment of severity, relationship to study drug (assessed only by those with the training and authority to make a diagnosis), and time of resolution/stabilization of the event. All AEs occurring while on study must be documented appropriately regardless of relationship. All AEs will be followed to adequate resolution.

Any medical condition that is present at the time that the subject is screened will be recorded in the Medical History eCRF and will be considered as Baseline and not reported as an AE. However, if the study subject's condition deteriorates at any time during the study, it will be recorded as an AE.

Changes in the severity of an AE will be documented to allow an assessment of the duration of the event at each level of severity to be performed. AEs characterized as intermittent require documentation of onset and duration of each episode.

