This study demonstrated that daily topical treatment of BTX 1204 4% (w/w) Solution BID was safe and well tolerated. No early discontinuations occurred as a result of an AE. There were no SAEs reported and the most common AEs were general disorders and administration site conditions including application site erythema, application site pruritus, and application site pain.

In studies conducted with BTX 1503, a formulation similar to BTX 1204 but with a drug load of 5% (w/w), facial dryness and facial itchiness were reported as possible effects of the study drug treatment in a healthy volunteer study (BTX.2017.001). In an acne study (BTX.2017.002), slight to moderate erythema was reported most frequently in cutaneous tolerability assessments. However, most subjects that reported erythema pre-or post-study drug application had erythema at Baseline and treatment with BTX 1503 did not exacerbate the erythema. Only 1 subject had increased erythema from Baseline and this was reported at Day 35, seven days after their final application of study drug. Slight scaling was reported in 2 subjects (9.5%), slight dryness was reported in 4 subjects (19.0%) and slight burning/stinging was reported in 5 subjects (23.4%). Only one positive cutaneous tolerability assessment (slight dryness) was reported at more than a single visit.

There is adequate support for evaluating the use of BTX 1204 4% (w/w) Liquid Formulation in this clinical study based on the findings observed in nonclinical and clinical studies conducted by Botanix Pharmaceuticals and its active ingredient CBD along with the extensive published literature on the use of CBD in multiple settings.

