4. STUDY ENROLLMENT AND WITHDRAWAL

4.1. Inclusion Criteria

To be included in the study, subjects must meet the following inclusion criteria.

1. Subject is of either gender between 12 and 70 years of age, inclusive.
2. Subject (or parent/legal guardian) has the ability and willingness to sign a written informed consent.
3. Subject has a diagnosis of chronic (≥ 1 year), stable atopic dermatitis (AD) according to Hanifin and Rajka [Hannifin 1980]
4. Subject has $\geq 5\%$ and $\leq 30\%$ body surface area (BSA) of AD involvement excluding the scalp and groin.
5. Subject has an Investigator's Global Assessment (IGA) score of moderate (3) atopic dermatitis on the 5-point IGA (0-4) scale.
6. For selected photography sites, subject has a target lesion 25 to 200 cm² in surface area on the trunk, upper extremities or lower extremities with a Baseline Signs of AD score of ≥ 6 and ≤ 12 .
7. Subject is in good general health without clinically significant hematological, cardiac, respiratory, renal, endocrine, gastrointestinal, psychiatric, hepatic, or malignant disease, as determined by the investigator.
8. Subject has suitable venous access for blood sampling.
9. Subject is able and willing to complete the study and to comply with all study instructions and attend the necessary visits.
10. Male subjects and their partners must agree and commit to use a barrier method of contraception throughout the study and for 90 days after last study drug application.
11. A negative urine pregnancy test (UPT) result for all WOCBP at the Screening Visit and Baseline Visit. A WOCBP is one who is not permanently sterilized or not postmenopausal. Postmenopausal is defined as 12 months with no menses without an alternative medical cause.
12. Sexually active women must agree to use the following throughout the study and for 30 days after last study drug application. WOCBP who are not sexually active at Baseline and become sexually active must identify a plan for contraception.
 - a. One of these highly effective contraception methods
 - i. Intrauterine device (IUD); hormonal (injections, implants, transdermal patch, vaginal ring; tubal ligation; partner vasectomy, OR
 - b. Oral contraceptives WITH a barrier method (listed below), OR
 - c. Two barrier forms of contraception (listed below)
 - i. Male or female condom; diaphragm; cervical cap; contraceptive sponge.

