5.1.8. Duration of Therapy

Subjects will receive BID application of study drug for 84 days with a final application on the evening of Day 84 for a total of 168 doses. If the Day 85 Visit is delayed, the subject should continue dosing through the evening before the scheduled Day 85 Visit.

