6.3.7. Day 85 Visit/End of Study Visit

The final application of study drug will occur on the evening prior to the Day 85 Visit. If the Day 85 visit is delayed, the subject should continue BID application until the evening before the Day 85 Visit. At the Day 85 Visit (Day 85 \pm 5 days), the following will be conducted:

- Collect and weigh returned study drug pumps
- Collect study diary
- Query subject for adverse events that occurred since the previous visit
- Query subject for changes in concomitant medications
- Collect blood sample for CBC and chemistry
- Collect urine sample for urinalysis
- Conduct UPT (WOCBP only)
- Perform IGA
- Calculate BSA of total AD involvement
- Assess Signs of AD score
- Collect EASI score
- Collect I-NRS
- Photographs and Signs of AD scoring of target lesion (selected sites only)
- Discharge subject from study

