7.4.3. Reporting of Pregnancy

As part of the eligibility criteria, WOCBP must agree to use appropriate contraception methods to avoid pregnancy during the study. If a subject does become pregnant, or is suspected of being pregnant, the subject will be immediately withdrawn from any further treatment with the study drug. The pregnancy, or suspected pregnancy will be immediately reported to the Medical Monitor.

Any subject that becomes pregnant during the study will be followed to term to collect pregnancy outcomes pending acquisition of the subject's permission. Pregnancy will be followed until the outcome of the pregnancy is known (i.e. miscarriage, abortion or birth), and the newborn condition is reported. No further follow up is required after birth unless specifically requested by the medical monitor. It will be the responsibility of the study's Medical Monitor to follow the subject after the subject's withdrawal from the study.

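### Pregnancy reporting ends with the study at Day 85 and omits male subjects' partners, although the protocol requires contraception for 30 and 90 days after the last application

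*Protocol*

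**What the plan says.** - **End of AE recording.** Protocol 7.3: "All AEs occurring after signing of the consent form through completion of Day 85 Visit will be recorded". Protocol 3.2 describes the same period as running from consent to the end of the study.
- **Last application.** Protocol 5.1.8 describes twice-daily treatment for 84 days, "with a final application on the evening of Day 84 for a total of 168 doses". Protocol 6.3.7 ties it to the visit: "The final application of study drug will occur on the evening prior to the Day 85 Visit". If the visit is delayed, dosing continues to the evening before it.
- **After the visit.** The last item in 6.3.7 is "Discharge subject from study". The schedule in 6.3.9 (Table 4) has no later visit or call, and its last pregnancy test is at Day 85.
- **Contraception.** Inclusion 12: "Sexually active women must agree to use the following throughout the study and for 30 days after last study drug application". Inclusion 10 has male subjects and their partners "use a barrier method of contraception throughout the study and for 90 days after last study drug application". Inclusion 13 bars sperm donation over the same 90 days.
- **Pregnancy reporting.** Protocol 7.4.3: "Any subject that becomes pregnant during the study will be followed to term to collect pregnancy outcomes", subject to her permission, through to the newborn's condition. Partners of male subjects are not mentioned.
- **Rules with no end date.** Protocol 7.4.2 requires SAEs to reach the sponsor within 24 hours of awareness and has AEs followed to resolution or stabilization. SAP 6.11.2 defines treatment-emergent events by onset on or after the first application, with no upper limit. SAP 6.1.3 excludes data from early-termination and unscheduled visits after study day 98.

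**The concern.** The inclusion criteria treat reproductive exposure as needing precautions for 30 days after treatment in women and 90 days in men. The reporting rules do not follow the same periods. If a precaution fails after Day 85, no section says that the pregnancy is to be reported. If a male subject's partner becomes pregnant, no section says so even while he is on treatment.

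The trial's objective includes safety. A final report showing no pregnancy exposures would be hard to interpret, because for most of the protocol's own precaution period nobody was due to ask or report. The open-ended SAE and treatment-emergent definitions add a smaller problem: two sites, or two programmers, could treat the same late event differently.

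**Working it through.** **Reproducing the plan's own figures.** Screening of up to 28 days plus 84 days of treatment gives 28 + 84 = 112 days, the stated maximum in the Protocol Summary, which leaves 0 days for follow-up. Doses: 84 × 2 = 168, as stated in 5.1.8.

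**Days without planned collection.** Let V be the day of the final visit. The last application is on day V − 1, and new-event recording closes on day V. A post-treatment period of length L ends on day V − 1 + L, so the part after closure is (V − 1 + L) − V = L − 1 days. The visit window in 6.3.7 is Day 85 ± 5.

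| Final visit | Last application | 30-day period ends | Days uncovered | 90-day period ends | Days uncovered |
|---|---|---|---|---|---|
| Day 80 | Day 79 | Day 109 | 29 of 30 | Day 169 | 89 of 90 |
| Day 85 | Day 84 | Day 114 | 29 of 30 | Day 174 | 89 of 90 |
| Day 90 | Day 89 | Day 119 | 29 of 30 | Day 179 | 89 of 90 |

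The visit window does not change the result, because the last application moves with the visit.

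**Does the pregnancy rule reach past Day 85?** Inclusions 10 and 12 name the study and the days after the last application as two separate stretches of time, and the subject is discharged at Day 85. A rule limited to pregnancies arising during the study therefore does not naturally cover the later stretch.

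**Against the SAP.** The Day 98 limit is 98 − 84 = 14 days after a nominal last application. The 30-day period ends 114 − 98 = 16 days beyond it. Data from an unscheduled visit late in that period would be excluded under 6.1.3, while 6.11.2 sets no end for treatment-emergent events.

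The expected number of pregnancies cannot be calculated: the documents give neither the sex split nor a conception rate. The size is therefore stated in days.

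**The case against.** The strongest reply is that this is an accepted design choice. The product is topical, and Protocol 1.3.1 describes limited systemic exposure in the healthy-volunteer study. Nothing in the documents requires a general post-treatment AE period. That stands: whether to add a safety contact, and how long after treatment, is a trade-off for the sponsor. It does not answer the mismatch between the protocol's precaution periods and its reporting rule.

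A reader might also infer stronger claims, which the documents do not support:

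- **That late events can never be collected.** Protocol 7.4.2 puts no end date on SAE reporting, and AEs already recorded are followed past Day 85 where needed. What is missing is planned collection of new events.
- **That the protocol has a 7-day post-treatment risk period.** The source is one observation in the acne study: "Only 1 subject had increased erythema from Baseline and this was reported at Day 35, seven days after their final application of study drug". It was a tolerability finding with BTX 1503, a similar formulation at 5%. It shows only that late skin findings can occur.
- **That 30 and 90 days are general AE windows.** They are contraception and sperm-donation rules, and bear on pregnancy exposure.
- **That Day 85 laboratory abnormalities are lost because results return after recording closes.** The rule in 7.3 turns on when an event occurs. Section 7.1.1 counts an abnormal laboratory finding as a possible AE, and Protocol 9.3.2 and SAP 6.11.4 summarize and list the results in any case.
- **That the 90-day rule rests on the testicular findings in animals.** Protocol 1.3.1 mentions that literature, calls its clinical relevance uncertain and says the sponsor's own studies did not show it. Inclusions 10 and 13 give no rationale.

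**Conclusion.** The point holds in a limited form. For completers, recording of new AEs closes about one day after the last application and no later contact is scheduled. Pregnancy reporting is confined to subjects and to the study period, so 29 of the protocol's own 30 days for women and 89 of its 90 days for men have no planned collection of pregnancy exposures. Partners of male subjects have no reporting rule at any time.

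This assumes that the study ends for a subject at the Day 85 discharge and that dosing runs to the evening before. A subject who stopped study drug earlier may have a longer off-drug interval before the termination assessment, so the one-day gap does not describe every one of the approximately 200 subjects. The efficacy analysis is unaffected. The pregnancy change is a cheap improvement to the safety data; general AE follow-up remains a matter of judgement.

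**What to change.** 1. **Protocol 7.4.3.** Reconcile it with inclusions 10, 12 and 13. Require reporting of pregnancies in subjects during the study and through the protocol's 30-day period. Require reporting, with the partner's permission, of pregnancies in partners of male subjects during the study and through the 90-day period. Tell subjects at the Day 85 Visit how to report, since discovery would otherwise depend on chance.
2. **Protocol 7.3 and 7.4.2.** State the date after which SAEs no longer need to be reported.
3. **SAP 6.11.2.** Give treatment-emergent events an end date consistent with the Day 98 limit in 6.1.3. If the sponsor chooses a later date, amend both sections together.
4. **Optional.** Consider one brief post-treatment safety contact, at a time set by the sponsor, and tabulate events found there separately. A single call around 30 days would not establish partner pregnancies through 90 days, so it does not replace item 1.

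Cost: a protocol and SAP amendment, consent wording and a partner-permission process, with follow-up work only when a pregnancy occurs. If the contact is added, there is also one call per subject and a later end to safety data collection. Day 85 stays the efficacy visit.
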